#### 9.7.1.6.4 FORMAL ANALYSES OF ORR, PFS, AND OS

A formal analysis will be carried out after all subjects have been enrolled and on study treatment for at least 6 months or have discontinued due to disease progression, death, or toxicity. Since the primary endpoint ORR data are expected to be observed sooner than the secondary endpoints, the timing of the formal analysis is chosen such that the secondary endpoints, PFS and OS, will be adequately described. The primary population for efficacy and safety analyses is the FAS.

#### 9.7.1.6.5 SENSITIVITY ANALYSES

The above efficacy analyses will be conducted in the EAS as sensitivity analyses.

#### 9.7.1.7 Pharmacokinetic, Pharmacodynamic, Pharmacogenomic, and Other Biomarker Analyses

##### 9.7.1.7.1 PHARMACOKINETIC ANALYSES

A population PK approach will be used to characterize the PK of lenvatinib and everolimus and the final PK model will be used to derive lenvatinib and everolimus exposure parameters to be used in the subsequent pharmacokinetic (PK)/pharmacodynamic analyses. The analyses will be detailed in a separate analysis plan. Concentrations of each analyte will be graphed by time within each nominal collection interval. Average dose at each collection interval will also be displayed.

##### 9.7.1.7.2 PHARMACOKINETIC/PHARMACODYNAMIC ANALYSES

Lenvatinib and everolimus exposure parameters derived from the population PK analysis will be related to biomarker, safety, and efficacy data using a model-based approach. For some

PK/pharmacodynamic analyses, data from this study may be pooled with data from other clinical studies of study drug.

For efficacy, a tumor growth inhibition model based on longitudinal tumor size measurements of target lesions will be included. We plan to explore exposure to both lenvatinib and everolimus exposure and/or selected biomarkers, identified in other studies of study drug, as predictors and/or correlations with tumor burden changes in the tumor growth inhibition model. Other analyses will include logistic regression analysis for ORR24W.

For the exposure-response relationship of safety, data will be analyzed using a longitudinal categorical logistic regression analysis for AEs leading to dosing reduction or interruption.

For the exposure-response relationship for selected biomarkers, identified in other clinical studies of study drug, data may be analyzed using a model-based approach.

Population PK and PK/pharmacodynamic analyses will be detailed in a separate analysis plan.

#### **9.7.1.7.3 PHARMACODYNAMIC, PHARMACOGENOMIC, AND OTHER BIOMARKER ANALYSES**

Soluble, tissue, genetic and/or imaging biomarkers (Baseline and/or posttreatment) may be summarized using descriptive statistics and correlated with clinical outcomes-related endpoints for safety and/or efficacy as appropriate. Details will be included in a separate analysis plan.

#### **9.7.1.8 Safety Analyses**

Safety, using the FAS, will be assessed by monitoring and recording of all AEs including all CTCAE grades, regular monitoring of hematology and clinical chemistry, urinalysis, regular measurement of vital signs, 12-lead ECGs, and performance of physical examinations.

Adverse events and other clinical safety data will be summarized descriptively in the FAS. The incidence of TEAEs, SAEs, drug-related AEs, and AEs leading to discontinuation will be summarized in tabulation. Hematology, serum chemistry, vital sign variables and ECG will be summarized descriptively for observed values, by grade and by change from Baseline by cycle. All AEs and lab parameters will be listed.

##### **9.7.1.8.1 EXTENT OF EXPOSURE**

The number of cycles/days on treatment, quantity of study treatment administered, and the number of subjects requiring dose reductions, treatment interruption, treatment delay, and treatment discontinuation due to adverse events will be summarized for each study drug.

##### **9.7.1.8.2 ADVERSE EVENTS**

The AE verbatim descriptions (investigator terms from the CRF) will be classified into standardized medical terminology using the Medical Dictionary for Regulatory Activities

(MedDRA). Adverse events will be coded to the MedDRA (Version 17 or higher) lower level term (LLT) closest to the verbatim term. The linked MedDRA preferred term (PT) and primary system organ class (SOC) are also captured in the database.

A treatment-emergent adverse event (TEAE) is defined as an AE that emerges during treatment, having been absent at pretreatment (Baseline) or

- Reemerges during treatment, having been present at pretreatment (Baseline) but stopped before treatment, or
- Worsens in severity during treatment relative to the pretreatment state, when the AE is continuous.

Only those AEs that are treatment-emergent will be included in summary tables. All AEs, treatment-emergent or otherwise, will be presented in subject data listings.

The TEAEs will be summarized. The incidence of TEAEs will be reported as the number (percentage) of subjects with TEAEs by SOC and PT. A subject will be counted only once within an SOC and PT, even if the subject experienced more than 1 TEAE within a specific SOC and PT. The number (percentage) of subjects with TEAEs will also be summarized by maximum severity (mild, moderate, or severe by highest CTCAE grade).

The number (percentage) of subjects with TEAEs will also be summarized by relationship to each study drug and combined (Yes [related] and No [not related]).

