**Table 3 Lenvatinib-Everolimus Combination Therapy Dose Reduction and Interruption Instructionsa**

Lenvatinib/Everolimus Treatment-Related Toxicity b,c Including Hepatic Injury and Thromboembolic Events	During Therapy	Adjusted Dose
		event onset, discontinue.
Fourth occurrence	Interrupt lenvatinib and everolimus	Discuss with sponsor
Grade 4g: Discontinue lenvatinib and everolimus		

Note: For grading see Common Terminology Criteria (CTC) for Adverse Events (AE) version 4.03. Collect all CTC grades of AEs, decreasing and increasing grade.

a: A delay of lenvatinib/ everolimus treatment for more than 28 days (due to lenvatinib/ everolimus-related toxicities) requires a discussion with the sponsor before treatment may be resumed.

b: Excluding alopecia. Drug interruption and dose reduction may be initiated for intolerable Grade 2 and Grade 3 related symptoms such as anemia, lymphocytopenia, asymptomatic neutropenia if there are no other treatment options available and the investigator considers that dose interruption or reduction of study medication is the only remaining alternative. Optimal medical management for nausea, vomiting, and/or diarrhea have to be initiated prior to any lenvatinib/ everolimus interruption or dose reduction.

c: Applicable only to Grade 2 toxicities judged by the subject and physician to be intolerable. If Grade 2 toxicity is determined to be intolerable, the dose of study drug will be reduced with or without dose interruption. Interruption for Grade 3 toxicities is mandatory.

d: Obese subjects with weight loss requiring dose interruption and reduction do not need to return to baseline or Grade 1 weight loss to restart lenvatinib. Based on the judgment of the investigator, subjects may be restarted at the lower dose of lenvatinib once the weight has been stable for at least 1 week. Normal body mass index (BMI) should be used as the new baseline for future dose reductions.

e: Not applicable to abnormal clinical laboratory values that are not clinically relevant based on the judgment of the investigator (eg, alanine aminotransferase (ALT), aspartate aminotransferase (AST), gamma glutamyl transpeptidase ( $\gamma$ -GTP) values  $< 10 \times$  upper limit of normal (ULN), and Na).

f: For hematologic toxicities, restart treatment after toxicity resolves to Grade 2.

g: Excluding laboratory abnormalities judged to be nonlife-threatening, in which case have to be managed as Grade 3.

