## **Assessing Severity of Adverse Events**

Adverse events will be graded on a 5-point scale according to Common Terminology Criteria for Adverse Event (CTCAE v4.03). Investigators will report CTCAE grades for all AEs (for both increasing and decreasing severity).

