## **Appendix 5      Common Terminology Criteria for Adverse Events (v4.03)**

The National Cancer Institute's CTCAE v4.0 published 28 May 2009 (v4.03: June 14, 2010) provides descriptive terminology to be used for AE reporting in clinical trials. A brief definition is provided to clarify the meaning of each AE term. To increase the accuracy of AE reporting, all AE terms in CTCAE version 4.0 have been correlated with single-concept, MedDRA terms.

Grades in CTCAEs v4.03 refer to the severity of the AE. Grades of 1 through 5, with unique clinical descriptions of severity for each AE, are based on this general guideline:

Grade	CTCAE Status
1	Mild: asymptomatic or mild symptoms; clinical or diagnostic observations only; intervention not indicated.
2	Moderate: minimal, local, or noninvasive intervention indicated; limiting age- appropriate instrumental activities of daily living (ADL). a
3	Severe or medically significant but not immediately life-threatening: hospitalization or prolongation of hospitalization indicated; disabling, limiting self-care ADL. b
4	Life-threatening consequences: urgent intervention indicated.
5	Death related to adverse event.

CTCAE = Common Terminology Criteria for Adverse Events.

a: Instrumental ADL refers to preparing meals, shopping for groceries or clothes, using the telephone, managing money, etc.

b: Self-care ADL refers to bathing, dressing and undressing, feeding self, using the toilet, taking medications, and not bedridden.

Adapted from the Cancer Therapy Evaluation Program, NCI. CTCAE v4.0. Available from:  
<http://evs.nci.nih.gov/ftp1/CTCAE/About.html> (Accessed 02 Oct 2014).

For further details regarding MedDRA, refer to the MedDRA website at:  
<http://www.meddramsso.com>. CTCAE v4.0 is available online at:  
<http://evs.nci.nih.gov/ftp1/CTCAE/About.html> (Accessed 02 Oct 2014).

## Appendix 6

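### The only TEAE severity summary the protocol states names three levels for a five-grade scale, so Grades 4 and 5 would probably be pooled with Grade 3

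*Protocol*

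**What the plan says.** Section 9.7.1.8.2 (Adverse Events) plans TEAE incidence by system organ class and preferred term. It adds that the number and percentage of subjects with TEAEs will be "summarized by maximum severity (mild, moderate, or severe by highest CTCAE grade". No other sentence in the protocol describes a summary of TEAEs by severity or grade.

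The data come in on a finer scale. Section 9.5.1.4.1, under Assessing Severity of Adverse Events, says: "Adverse events will be graded on a 5-point scale according to Common Terminology Criteria for Adverse Event (CTCAE v4.03". Appendix 5 repeats this ("Grades of 1 through 5, with unique clinical descriptions of severity for each AE, are based on this general guideline") and labels Grade 1 as mild and Grade 2 as moderate. Its labels for the upper three grades are:

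- Grade 3: "Severe or medically significant but not immediately life-threatening"
- Grade 4: "Life-threatening consequences: urgent intervention indicated"
- Grade 5: "Death related to adverse event"

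The other planned adverse event tables are in Section 9.7.1.8: "The incidence of TEAEs, SAEs, drug-related AEs, and AEs leading to discontinuation will be summarized in tabulation". None of them is described as split by grade. For laboratory data, by contrast, Section 9.7.1.8.3 does call for a summary by CTCAE grade.

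**The concern.** The parenthesis in Section 9.7.1.8.2 borrows the Appendix 5 labels for the first three grades and stops there. A programmer who follows it has no stated place for a subject whose worst event was Grade 4 or 5. Putting that subject under *severe* goes against Appendix 5, where the word means not immediately life-threatening.

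Safety and tolerability is a secondary objective (Section 8.2), and with a single arm the safety result is purely descriptive. Whether high-grade toxicity was severe, life-threatening or fatal is a basic part of that description. The protocol itself treats the boundary as meaningful: Table 3 in Section 9.4.1.1 gives Grade 4 its own row ("Discontinue lenvatinib and everolimus"), apart from Grade 3. What is at stake is how clear one safety table is.

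**Working it through.** The protocol states no figure on this point, so there is none to reproduce. The check sets the collected scale beside the reporting levels.

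| CTCAE grade | Meaning in Appendix 5 | Level named in Section 9.7.1.8.2 |
|---|---|---|
| 1 | mild | mild |
| 2 | moderate | moderate |
| 3 | severe, not immediately life-threatening | severe |
| 4 | life-threatening | none |
| 5 | death | none |

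Five grades are collected and three levels are named, so 5 − 3 = 2 grades have no level.

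**How the sentence can be read**

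1. *Pooling.* Grades 3, 4 and 5 all go under *severe*. The sentence covers subjects with TEAEs without excluding any grade, and it classifies by highest CTCAE grade. This is the most natural literal reading. It contradicts the Appendix 5 meaning of the word and hides the split between the three upper grades.
2. *Full grade table.* The classifier is the grade itself, and the three words are a loose gloss. This may well have been the intent, but the words do not say so.
3. *Exclusion.* Subjects whose worst event was Grade 4 or 5 do not appear. This has little support, for the reasons given under reading 1.

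Readings 1 and 2 give different tables from the same sentence.

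**What the other outputs recover**

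- *SAE table (Section 9.7.1.8).* Under Section 9.5.1.4.2, serious events include fatal and life-threatening ones. They also include hospitalization, disability and all clinically significant bleeding, so seriousness does not stand in for grade.
- *AEs leading to discontinuation.* Treatment-related Grade 4 toxicity leads to discontinuation under Table 3. Footnote g excepts laboratory abnormalities judged not life-threatening.
- *End-of-study status (Section 9.7.1.3).* Deaths are counted. Progression is not recorded as an adverse event (Section 9.5.1.4), so this count is not a count of Grade 5 events.
- *Laboratory summaries (Section 9.7.1.8.3).* These are by CTCAE grade, but only for laboratory parameters.
- *Listings.* All adverse events are listed, and with about 31 subjects each high-grade event can be found.

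The information therefore survives, but none of these outputs is a TEAE summary by grade.

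**The case against.** The strongest reply has three parts.

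*The phrase already points to grade.* It says the classification is by highest CTCAE grade, so the three adjectives may be no more than shorthand. This stands in part. It makes exclusion of Grades 4 and 5 unlikely and suggests that a grade table was intended. It does not remove the ambiguity, because the words listed stop at Grade 3.

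*Table layout belongs in the SAP.* Section 9.7 does defer details to a SAP, which is not at hand and may already use five grades. Had the protocol been silent, there would be no point to raise. But it names the levels, and the names conflict with its own scale. Section 9.7.5 says that departures from the protocol's analysis plan are documented in the SAP, so a five-grade table might have to be recorded there as one.

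*Serious outcomes are reported elsewhere.* This stands, and it is the main reason why the impact is small.

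A reader might also infer more than the text supports:

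- *That life-threatening and fatal events would be left out.* Nothing in the sentence excludes any grade.
- *That the table could not be set beside Study 205.* Section 7.1.4.2 quotes that study's figures already combined over Grades 3 and 4. A pooled *severe* row differs from that format only by including any Grade 5 event.
- *That the tolerability objective goes unanswered.* The tables for serious events, discontinuations, exposure and laboratory values all bear on it.
- *That the Study 205 rate sizes the problem.* Taking 71% of 31 subjects (0.71 × 31 ≈ 22) counts subjects with Grade 3 and 4 events together. It says nothing about how many are Grade 4 or 5, which is the only information at risk. It also comes from pretreated clear-cell patients.

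**Conclusion.** The inconsistency is real and minor. As written, Section 9.7.1.8.2 gives no named level to two of the five grades that the protocol collects. The likely result is that Grades 3, 4 and 5 are pooled under a word that Appendix 5 reserves for events that are not immediately life-threatening. The only TEAE severity summary stated in the protocol could then not separate severe, life-threatening and fatal events.

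That pooling is the likely outcome is a judgement about how the sentence would be programmed; the SAP may settle it differently. The number of subjects affected cannot be estimated, because the protocol gives no split of Grade 4 or Grade 5 from Grade 3. No data are lost, and the response-rate test, its type I error and its power do not depend on this table.

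**What to change.** In Section 9.7.1.8.2, replace the parenthesis with: *by highest CTCAE grade (Grade 1, 2, 3, 4, 5), with Grade 3 or higher also shown*. The combined row keeps a high-grade total, and the separate rows show life-threatening and fatal events. If the SAP already tabulates all five grades, the change only brings the protocol into line with it.

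The cost is one line of text. The grades are already recorded for every adverse event, so no new data, procedure or visit is needed, and nothing changes for subjects.

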#### 9.7.1.8.3 LABORATORY VALUES

Clinical laboratory (ie, hematology, serum chemistry, and qualitative urinalysis) values will be evaluated for each laboratory parameter. Abnormal laboratory values will be flagged and identified as those outside (above or below) the normal range. Reference (normal) ranges for laboratory parameters will be included in the clinical study report for this protocol.

Descriptive summary statistics (eg, n, mean, standard deviation, median, minimum, maximum for continuous variables; n[%] for categorical variables) for laboratory parameters and their changes from baseline will be calculated. Laboratory values will be summarized by visit and by worst postbaseline visit.

Laboratory parameters that are graded in CTCAE (v4.03) will be summarized by CTCAE grade. In the summary of laboratory parameters by CTCAE grade, parameters with CTCAE grading in both high and low directions (eg, calcium, glucose, magnesium, potassium, sodium) will be summarized separately.

Please see Appendix 7 for sponsor's grading of laboratory values.

#### 9.7.1.8.4 VITAL SIGNS

Descriptive statistics for vital signs parameters (ie, systolic and diastolic BP, pulse, respiratory rate, temperature, and weight) and changes from baseline will be presented by visit for all visits. Vital signs will be listed by subject and visit.

#### 9.7.1.8.5 ELECTROCARDIOGRAMS

ECG assessments will be performed at the Screening Visit and during the Treatment Phase according to Table 5. Descriptive statistics for ECG parameters and changes from baseline will be presented by visit.

#### 9.7.1.8.6 OTHER SAFETY ANALYSES

Not applicable.

#### 9.7.1.9 Other Analyses

Any other statistical/ analytical issues will be discussed in the SAP.

### 9.7.2 Determination of Sample Size

The sample size is calculated using Simon's Two-Stage Design for the primary endpoint ORR assuming an ORR of 25% from this study versus an historical control of 8%. A total of approximately 31 subjects, including 16 in Stage 1, are planned to be enrolled in the study. The actual number of subjects accrued will depend on the results from Stage 1. If  $\leq 1$  responders are observed in the first 16 subjects treated (Stage 1), the enrollment will be stopped. The total sample size will be the actual number of subjects enrolled at the time of termination of the study. If  $\geq 2$  responders are observed in Stage 1, the study will proceed to Stage 2 and a total of 31 subjects will be enrolled. At least 6 responders in 31 subjects is required to claim superiority of the study treatment. This design yields a one-sided type I error of 0.0319 and the power of 0.8053 in Stages 1 and 2 combined.

### 9.7.3 Interim Analysis

An interim analysis may be performed by the sponsor after 16 subjects in Stage 1 have completed at least 2 tumor assessments (eg, Week 16 tumor assessments), unless discontinued due to disease progression, death or toxicity. If one or no responders are observed in the interim analysis, the study will be stopped early for futility and subjects on study at that time will continue treatment under the discretion of the investigator. If two or more responders are confirmed before the planned interim analysis and the safety profiles of both drugs are acceptable, the study will continue to Stage 2 and a formal interim analysis may be waived. There will be no enrollment gap for the interim analysis.

At interim analysis, the probabilities of early futility stopping are 0.6299 under  $H_0$ : ORR=8% and 0.0635 under  $H_a$ : ORR $\geq 25\%$ , respectively.

### 9.7.4 Other Statistical/Analytical Issues

None.

#### 9.7.5 Procedure for Revising the Statistical Analysis Plan

The SAP will be finalized prior to the database lock in this study. Any deviation from the analysis plan described in the protocol will be documented in the SAP.

## **11 PROCEDURES AND INSTRUCTIONS (ADMINISTRATIVE PROCEDURES)**

### **11.1 Changes to the Protocol**

Any change to the protocol requires a written protocol amendment or administrative change that must be approved by the sponsor before implementation. Amendments specifically affecting the safety of subjects, the scope of the investigation, or the scientific quality of the study require submission to health or regulatory authorities as well as additional approval by the applicable IRBs/IECs. These requirements should in no way prevent any immediate action from being taken by the investigator, or by the sponsor, in the interest of preserving the safety of all subjects included in the study. If the investigator determines that an immediate change to or deviation from the protocol is necessary for safety reasons to eliminate an immediate hazard to the subjects, the sponsor's medical monitor and the IRB/IEC for the site must be notified immediately. The sponsor must notify the health or regulatory authority as required per local regulations.

Protocol amendments that affect only administrative aspects of the study may not require submission to health or regulatory authority or the IRB/IEC, but the health or regulatory authority and IRB should be kept informed of such changes as required by local regulations. In these cases, the sponsor may be required to send a letter to the IRB/IEC and the Competent Authorities detailing such changes.

### **11.2 Adherence to the Protocol**

The investigator will conduct the study in strict accordance with the protocol (refer to ICH E6, Section 4.5).

### **11.3 Monitoring Procedures**

The sponsor's/CRO's CRA will maintain contact with the investigator and designated staff by telephone, letter, or email between study visits. Monitoring visits to each site will be conducted by the assigned CRA as described in the monitoring plan. The investigator will allow the CRA to inspect the clinical, laboratory, and pharmacy facilities to assure compliance with GCP and local regulatory requirements. The CRFs and subject's corresponding original medical records (source documents) are to be fully available for review by the sponsor's representatives at regular intervals. These reviews verify adherence to study protocol and data accuracy in accordance with local regulations. All records at the site are subject to inspection by the local auditing agency and to IRB/IEC review.

In accordance with ICH E6, Section 1.52, source documents include, but are not limited to, the following:

- Clinic, office, or hospital charts
- Copies or transcribed health care provider notes that have been certified for accuracy after production

- Recorded data from automated instruments such as IxRS, x-rays, and other imaging reports (eg, sonograms, CT scans, magnetic resonance images, radioactive images, ECGs, rhythm strips, electroencephalograms [EEGs], polysomnographs, pulmonary function tests) regardless of how these images are stored, including microfiche and photographic negatives
- Pain, quality of life, or medical history questionnaires completed by subjects
- Records of telephone contacts
- Diaries or evaluation checklists
- Drug distribution and accountability logs maintained in pharmacies or by research personnel
- Laboratory results and other laboratory test outputs
- Correspondence regarding a study subject's treatment between physicians or memoranda sent to the IRBs/IECs
- CRF components (eg, questionnaires) that are completed directly by subjects and serve as their own source.

